10.4 Interim Analysis/Criteria for Stopping Study

10.4.1 Safety Criteria

The first 6 patients will be part of an initial safety run-in. A safety analysis will be done after all six patients have been observed for at least 2 weeks after completion of cycle 1. All toxicities will be tabulated. The study will move forward if ≤ 1 of 6 in the safety lead in cohort 1 experience a DLT (as defined in Section 4.3 and Table 3). If ≥ 2 of 6 in cohort 1 experience a DLT, the study will be suspended and an amendment to explore alternate dosing schemes will be considered. Toxicity counts and rates and the results of the analysis will be reviewed by the DMC. The patients enrolled in the safety lead in cohort will be included in the efficacy analysis.

10.4.2 Efficacy Criteria

As this is a two-stage design, an interim efficacy analysis is planned after 18 patients are evaluable (see 10.2 for additional details). After testing the drug on 18 patients in the first stage, consideration will be given to trial termination if 2 or fewer patients demonstrate clinical benefit (CR, PR, or SD for at least 3 months). If the trial goes on to the second stage, a total of **35 evaluable**

NU Study Number: NU 16G03

Merck Study Number: 3475-244

patients will be studied. If the total number responding is less than or equal to 6, the combination is rejected.

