Statistical Methodology	
This is a non-randomized, open label phase II study. Study endpoints are defined in Section 6.0
 
We will utilize the optimum two stage design, and we anticipate enrolling 35 evaluable patients. This two-stage design, which will test the null hypothesis that ORR<=0.10 versus the alternative that ORR>=0.30 (where ORR is calculated via RECIST v1.1), has an expected sample size of 22.5 and a probability of early termination of 0.71 when ORR=0.10. If the drug combination is actually not effective, there is a 0.047 probability of concluding that it is (the target for this value was 0.050). If the drug is actually effective, there is a 0.098 probability of concluding that it is not (the target for this value was 0.100). After testing the drug on 18 patients in the first stage, consideration will be given to trial termination if 2 or fewer patients demonstrate clinical benefit (CR, PR, or SD for at least 3 months). If the trial goes on to the second stage, a total of 35 evaluable patients will be studied. If the total number responding is less than or equal to 6, the combination is rejected. Subjects who are not evaluable for response will be replaced so that up to 46 subjects will be enrolled.

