10.2 Sample Size and Accrual

We will utilize the optimum two-stage design and we anticipate enrolling 35 evaluable patients. This two-stage design to test the null hypothesis that $RR \leq 0.10$ versus the alternative that $RR \geq 0.30$ (where RR is calculated via RECIST v1.1) has an expected sample size of 22.5 and a probability of early termination of 0.71 when $RR = 0.10$. If the drug combination is actually not effective, there is a 0.047 probability of concluding that it is (the target for this value was 0.050). If the drug is actually effective, there is a 0.098 probability of concluding that it is not (the target for this value was 0.100). Subjects who are not evaluable for response will be replaced so up to 46 subjects may be enrolled.

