10.3 Data Analysis Plans

10.3.1 Analysis Plans for Primary Objective

The primary outcome is objective response by RECIST v1.1. The proportion of patients having an objective response by RECIST 1.1 will be estimated with a 95% exact binomial confidence interval for the efficacy population. These confidence intervals will be adjusted for the sequential nature of the two-stage procedure ²⁴.

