NU Study Number: NU 16G03
Merck Study Number: 3475-244

Section 10.4.2 efficacy criteria in statistics section	interim analysis planned after 18 patients using Clinical Benefit(defined as CR,PR, or SD for at least 3 month).	Changed to state that interim analysis is planned with 18 patients using RR	Since primary objective is ORR.
Section 11.5 Instructions for Participating Sites	This section was not in the protocol.	Inserted this section after University of Chicago came on board as affiliate site	To include information for affiliate sites
Amendment 3 5/10/2017			
Sections(s) Affected	Prior Version	Amendment 3 Changes	Rationale
Study Schema	Tumor assessments every 2 cycles	Tumor assessments every 2 cycles up to cycle 5; then every 3 cycles	For safety and convenience
Section 2.2.4 Secondary objective	Statement of RR assessment with RECIST1.1 and irRC	Added language referring to section 6.0 which has new language regarding RECIST1.1 which will be used here with a few adaptations	For clarity and accuracy. To accommodate immune response adaptations of RECIST 1.1
Section 4.2 Treatment administration	Table containing details of administration of pembrolizumab and guadecitabine.	Added footnote: "After completion of the safety run in, starting on Day 5 of each cycle, growth factor support filgrastim or peg filgrastim can be administered 24 hours after completion of guadecitabine administration, at the discretion of the treating physician." Similar language added to section 4.4.1 which pertains to 'Dose modifications for guadecitabine'	For safety
Section 4.4.1 Dose modifications for Guadecitabine	In general, guadecitabine dosing should be held guadecitabine-related non-hematologic toxicities until toxicity has resolved to ≤	Modified to : In general, guadecitabine dosing should be held for ≥ Grade 3 neutropenia, thrombocytopenia or other guadecitabine-related non-hematologic toxicities until toxicity has resolved to ≤ Grade 1 or baseline levels	For clarity and safety

NU Study Number: NU 16G03
Merck Study Number: 3475-244

	Grade 1 or baseline levels		
Section 4.4.2 Table 3 Dose modification guidelines for pembrolizumab related AEs	Previous table which had the window for resolution of toxicity as ≤28 days of last dose.	Updated window to ≤28 days from the start of the event throughout the table and footnotes and notes. Similar update done in section 4.10	For safety and convenience

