Throughout (wherever applicable)	Previous statement about Guadecitabine priming followed by Pembrolizumab therapy, then monotherapy with pembrolizumab.	Language inserted: “For patients who discontinued guadecitabine for reasons other than toxicity (i.e. disease stability of response > 6 months) and progress on pembrolizumab alone, a re-trial of guadecitabine in combination with pembrolizumab is possible, at the discretion of the treating physician, if the patient is clinically stable.”	As an addendum to the provision of pembrolizumab monotherapy, in order to give patients another chance before taking them off study.
Section 1.1 Ovarian cancer background	Previous language	Some language deleted	Language not appropriate in this context.
Throughout	Secondary Objective stated as RR and ORR(for Objective Response Rate) in different sections of the protocol.	Corrected to ORR for Objective Response Rate	For consistency and accuracy

NU Study Number: NU 16G03
Merck Study Number: 3475-244

Section 4.1 Treatment overview	Details regarding Guadecitabine and Pembrolizumab combination therapy.	Inserted language regarding Guadecitabine skipped dose versus dose delay. Language regarding pembrolizumab monotherapy also inserted.	For clarity and consistency
Section 2.2.2, 6.3 10.4.2	Definition of Clinical Benefit rate inconsistent between study summary and rest of the protocol.	Language updated to match the statistical portion of the study summary. The correct plan is : "After testing the drug on 18 patients in the first stage, consideration will be given to trial termination if 2 or fewer patients demonstrate clinical benefit (CR, PR, or SD for at least 3 months)."	Correction of the discrepancy between the sections of the protocol it serves to clarify the initial intent of the two stage study design per the original sponsor-approved statistical plan.
Section 4.1 Treatment plan overview	Previous language for treatment administration	Added language to clarify scheduling details and skipped doses and dose delays.	For increased clarity
Section 4.4.1 Dose modifications for Guadecitabine	Previous language	Added details regarding grades for thrombocytopenia and Guadecitabine-related non-hematologic toxicities. Added other language for clarity.	For increased clarity

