Study summary and Section 10 Statistical considerations. (Sample size and statistics)	Maximum accrual was stated to be 38 in order to obtain 35 evaluable patients. (with an anticipated 1-3 patients that may be inevaluable).	Maximum accrual has been increased to 46 in order to obtain 35 evaluable patients. [This has been done after DSMC approved that 8 more patients can be added to reach 35 evaluable. This request to DSMC was based on the fact there were 5 patients who were enrolled and didn't start study treatment. There were another 7 patients who registered and only had one cycle of treatment, which meant that they were not evaluable for the primary end point. This is a total of 12 patients, when it was initially anticipated that only 1-3 patients would not be evaluable for response. Thus, it became essential to update the total enrollment to 46 in the hope that we will obtain 35 evaluable, with a drop out of 13-14 patients].	Based on the initial DSMC approval that this study can add up to 8 more patients to obtain a total of 35 evaluable patients.
Section 8.1 Drug Section: Pembrolizumab	Previous specifications regarding drug preparation.	Updated with most current specifications for drug preparation	Based on current IB and pharmacy manual.
Section 8.2 Drug section Guadecitabine	Previous specifications regarding drug preparation. and storage	Updated with most current specifications. [Astex sent notification that the current stock of 3ml diluent will be depleted by July 2019 and they will start supplying 1.2ml diluent around this timeframe. So, all documents need to be updated to reflect this.]	Based on updated pharmacy manual from Astex.

NU Study Number: NU 16G03
Merck Study Number: 3475-244

Section 11.9 Publication policy	Previous template language	Updated with most current template language for publication policy	Administrative.
------------------------------------	----------------------------	--------------------------------------------------------------------	------------------------

Protocol Amendment 10 – Version date: October 15, 2020			
Section	Prior Version	Changes in Amendment 10	Rationale
Cover page and throughout	Protocol amendment: 9 Protocol date: January 23, 2019	Protocol amendment: 10 Protocol date: October 15, 2020	Administrative update

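### The stated alpha 0.047, beta 0.098 and expected N 22.5 are those of an enforced stage-1 stop on objective responses; the stop as written is discretionary in wording, counts clinical benefit, and has no stated properties

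*Combined protocol and SAP*

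**What the plan says.** Section 10.2 and the Study Summary (Statistical Methodology) set an optimum two-stage design on RECIST 1.1 response rate, 0.10 against 0.30. The design "has an expected sample size of 22.5 and a probability of early termination of 0.71" at a response rate of 0.10. On error rates: "If the drug combination is actually not effective, there is a 0.047 probability of concluding that it is", and the matching figure for missing an effective combination is 0.098. The targets are 0.050 and 0.100.

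Section 10.4.2, repeated in the Study Summary, gives the rules. At 18 evaluable patients, "consideration will be given to trial termination if 2 or fewer patients demonstrate clinical benefit (CR, PR, or SD for at least 3 months"). At 35, the count is of responders: "If the total number responding is less than or equal to 6, the combination is rejected".

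For the primary estimate, Section 10.3.1 plans an exact 95% binomial interval for ORR and adds: "These confidence intervals will be adjusted for the sequential nature of the two-stage procedure". It does not say which stopping rule that adjustment assumes.

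No section gives the error rates, stopping probability or expected N of a stop based on clinical benefit, or an assumed rate of stable disease lasting 3 months or more.

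**The concern.** The two stages count different events against cut-offs that come from a design counting only one of them. A patient with stable disease for 3 months helps the trial pass stage 1 but does nothing for the final test. The cut-off of 2 was set for responses alone, so adding stable disease makes it easier to pass. The wording also leaves stopping to judgement, whereas the printed figures require the stop to happen whenever the count is met.

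The Study Summary puts the figures and the rule in one paragraph, so an IRB or monitoring committee will read the first as describing the second. They would conclude that at ORR 0.10 the trial ends at 18 patients about 7 times in 10. Limiting exposure to an inactive regimen is the purpose of a two-stage design, and this is the property most affected. The ORR interval is affected too if its adjustment assumes a stop on responses.

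**Working it through.** **Inputs.** From Sections 10.2 and 10.4.2: ORR 0.10 and 0.30; 18 patients at stage 1, cut-off 2; 35 in total, 7 or more responses needed for success. Assumed, because the documents give no figure: a rate s of stable disease of at least 3 months of 5, 10, 20 or 30%, the same at both ORRs.

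**Step 1: reproduce the printed figures, with an enforced stop on responses.**
- Stopping probability at ORR 0.10: P(Bin(18, 0.10) ≤ 2) = 0.9^18 + 18(0.1)(0.9^17) + 153(0.01)(0.9^16) = 0.1501 + 0.3002 + 0.2835 = 0.734.
- Expected N: 18 + 17 × (1 − 0.7338) = 22.53 (printed 22.5).
- Alpha: sum over x = 3 to 18 of P(Bin(18, 0.10) = x) × P(Bin(17, 0.10) ≥ 7 − x) = 0.0474 (printed 0.047).
- Power, by the same sum at 0.30: 0.9016, so beta is 0.0984 (printed 0.098).

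A grid search returns 18/2, 35/6 as the optimum for targets 0.05 and 0.10, so this is the design the figures came from. The printed 0.71 does not fit. It would give 18 + 17 × 0.29 = 22.9, while 22.5 implies 1 − 4.5/17 = 0.735.

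**Step 2: the rule as written, followed every time.** Stage-1 responses and stable disease are trinomial(18; ORR, s). The trial stops if their sum is 2 or fewer, so the stopping probability is P(Bin(18, ORR + s) ≤ 2). Success still needs 7 or more responses of 35.

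| s | Stopping prob., ORR 0.10 | Expected N, ORR 0.10 | Alpha | Power, ORR 0.30 |
|---|---|---|---|---|
| 0% | 0.734 | 22.5 | 0.0474 | 0.902 |
| 5% | 0.48 | 26.8 | 0.0515 | 0.923 |
| 10% | 0.27 | 30.4 | 0.0536 | 0.931 |
| 20% | 0.06 | 34.0 | 0.0549 | 0.935 |
| 30% | 0.008 | 34.9 | 0.0552 | 0.935 |

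At ORR 0.10, the stopping probability falls below the printed 0.71 once s exceeds about 0.5%, and below 0.50 above 4.6%. Alpha passes 0.050 above 2.8%.

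**Step 3: the stop is never enacted.** P(Bin(35, 0.10) ≥ 7) = 0.0552; P(Bin(35, 0.30) ≥ 7) = 0.935; N = 35. This bounds what discretion can do to alpha.

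**Step 4: the ORR interval.** An adjustment for an enforced stop on responses treats 35 patients with 2 or fewer responses as impossible. Under the clinical-benefit rule at ORR 0.10, that outcome has probability 0.07, 0.16, 0.27 or 0.30 for s = 5, 10, 20 or 30%. It can also happen under a response rule that is not enforced: if stopping is enacted half the time, the probability is 0.15. The ordinary exact interval, used under the clinical-benefit rule, has minimum coverage of about 0.952 for ORR 0.02 to 0.50 and s from 5 to 30%.

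**The case against.** The strongest reply is that counting clinical benefit is deliberate. The amendment log records at Amendment 2 "Changed to state that interim analysis is planned with 18 patients using RR", and then at Amendment 6 a return to clinical benefit, of which it says "it serves to clarify the initial intent of the two stage study design per the original sponsor-approved statistical plan". Continuing a regimen that holds disease stable may be exactly what is wanted. This stands. A reader might infer from the Amendment 2 entry that the current rule is a drafting error, but that entry describes superseded text and Amendment 6 reverses it. Intent does not, however, transfer another rule's properties to this one.

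A reader might also infer that the type I error is badly inflated or the primary test invalid. The figures do not support that. Alpha cannot exceed 0.0552, power rises, the 7-of-35 criterion is untouched, and the maxima of 35 evaluable and 46 enrolled are disclosed.

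Two cautions stand. The wording supports a discretionary reading but does not settle whether the stop was meant to bind. And the loss of futility protection depends on a stable-disease rate that the documents do not give: its direction is certain for any rate above zero, its size is not.

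Finally, the look may be over. Amendment 9 lists patients not evaluable for response: "This is a total of 12 patients, when it was initially anticipated that only 1-3 patients would not be evaluable for response". The cap was then 38. If accrual had reached it, 38 − 12 = 26 were evaluable, past the 18 needed. The log does not say that accrual was at the cap or that the look took place, so this is probable, not established.

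**Conclusion.** Wrong as written. The stated 0.047, 0.098 and 22.5 apply to the written rule only if no patient has stable disease of 3 months or more and the stop is enforced. The stated 0.71 is a separate slip, since the response rule gives 0.73. Under the written rule, always followed, the stopping probability at ORR 0.10 runs from 0.48 down to 0.008 over the assumed 5 to 30% range, and leaving the stop to discretion can only lower it further. The error is mainly one of overstated futility protection and understated expected sample size. The effect on alpha is small and there is no loss of power. The linked gap in Section 10.3.1 is real but narrow: the adjusted ORR interval fits only if it assumes the stopping rule actually used. The figures rest on exact enumeration, with the stable-disease rate assumed and held equal at both ORRs.

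**What to change.** In the Study Summary and Sections 10.2 and 10.4.2:
- State whether the stage-1 stop is binding.
- Replace the printed properties with those of the clinical-benefit rule, as a range over stable-disease rates: stopping probability and expected N as tabulated, alpha up to 0.055, power 0.90 to 0.935.
- If the response-count figures are kept for reference, label them as such and correct 0.71 to 0.73.

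If the look has taken place, report which count was applied and whether the stop was enforced, give the properties of that rule, and do not change the rule afterwards.

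In Section 10.3.1, name the stopping rule that the ORR interval assumes. An adjustment built on stopping for responses fits only if responses were counted and the stop was enforced. Otherwise use the ordinary exact binomial interval for ORR.

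Cost: text only, with no change to conduct, so it can be done at any time. The restated stopping probability, expected N and alpha will be less favourable than those now printed.

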11.0 STUDY MANAGEMENT

11.1 Institutional Review Board (IRB) Approval and Consent

It is expected that the IRB will have the proper representation and function in accordance with federally mandated regulations. The IRB should approve the consent form and protocol.

In obtaining and documenting informed consent, the investigator should comply with the applicable regulatory requirement(s), and should adhere to Good Clinical Practice (GCP) and to ethical principles that have their origin in the Declaration of Helsinki.

Before recruitment and enrollment onto this study, the patient will be given a full explanation of the study and will be given the opportunity to review the consent form. Each consent form must include all the relevant elements currently required by the FDA Regulations and local or state regulations. Once this essential information has been provided to the patient and the investigator is assured that the patient understands the implications of participating in the study, the patient will be asked to give consent to participate in the study by signing an IRB approved consent form.

Prior to a patient's participation in the trial, the written informed consent form should be signed and personally dated by the patient and by the person who conducted the informed consent discussion.

11.2 Amendments

The Principal Investigator will formally initiate all amendments to the protocol and/or informed consent. All amendments will be subject to the review and approval of the appropriate local, institutional, and governmental regulatory bodies, as well as by Merck and Astex.

11.3 Registration Procedures

11.3.1 Registering a Patient for the safety Run-in portion of the Study

For potential patients for the phase I portion of this study, study teams are asked to inform the QAM of the date and time that the patient will need to be registered ([contact]).

BEFORE a patient can be treated on study, please complete and submit the following items to confirm eligibility and receive an identification number:

- Patient's signed and dated informed consent form (upload to NOTIS and keep original hard copy in a secure location/study chart)
- Eligibility checklist (signed and dated by the treating physician – upload to NOTIS)
- Eligibility eCRF (complete in NOTIS)
- Copy of the pathology report (upload to NOTIS)

The QAM will review all source documentation required to confirm eligibility that is readily available in the patient's electronic medical record (EMR). Any information that is not available in the EMR must be de-identified and emailed to the QAM. Once the QAM confirms the patient is eligible, he or she will register the patient, assign a subject identification number, provide a cohort assignment, and send a confirmation of registration to involved personnel. Registration will then be complete and the patient may begin study treatment.

NU Study Number: NU 16G03

Merck Study Number: 3475-244

11.3.2 Registering a Patient to the Study (after safety run-in)

For potential patients enrolled after the safety run-in portion of this study, study teams are asked to inform the QAM of the date and time that the patient will need to be registered ([contact]).

BEFORE a patient can be treated on study, please complete and submit the following items to confirm eligibility and receive a subject identification number:

- Eligibility eCRF (complete in NOTIS)
- Eligibility checklist (signed and dated by the treating physician – upload in NOTIS)
- Signed and dated informed consent document (upload in NOTIS)
- Pathology Report (upload in NOTIS)

The QAM will review the registration, register the patient, assign an identification number, and send a confirmation of registration to involved personnel. Registration will then be complete and the patient may begin study treatment.

11.4 Data Submission

Once a subject is confirmed and registered to the study, eCRFs should be submitted according to the detailed data submission guidelines (provided in a separate document). Generally, all data for Safety run-in patients during the time period patients are evaluated for Dose Limiting Toxicities (DLTs) must be submitted on a weekly basis. Generally, for all phase II patients, data are due at the end of every cycle.

Please contact [contact] for further details.

11.5 Instructions for Participating Sites

Before the study can be initiated at any site, the following documentation must be provided to the Clinical Research Office at Northwestern University:

- Signed and completed Letter of Invitation to participate in the study.
- Signed copy of Northwestern University's Data Monitoring Committee policy pertaining to data submission.
- Draft informed consent form should for review/approval prior to submission to the local IRB
- A copy of the official IRB approval letter for the protocol and informed consent.
- CVs and medical licensure for the local PI and any sub-investigators who will be involved in the study at the site.
- Form FDA 1572 appropriately filled out and signed with appropriate documentation.

NU Study Number: NU 16G03
Merck Study Number: 3475-244

Additional activities may be required prior to site activation (i.e. contract execution, study-specific training). Full requirements will be outlined in a memo upon receipt of the signed Letter of Invitation.

